Participants who met the eligibility criteria and provided consent subsequently completed a 12-lead electrocardiogram stress test at a local cardiac rehabilitation clinic supervised by a certified exercise physiologist prior to beginning the intervention. Depending on each participant's baseline physical ability and/or comfort level with treadmills, the exercise physiologist employed a Bruce or Modified Bruce protocol for the stress test. Protocol stages were performed on a treadmill and incremented sequentially every 3 minutes until participants reached volitional exhaustion or the test was stopped by the exercise physiologist according to safety cut-offs (blood pressure >250/120, oxygen saturation <82%, physical concerns). Participants' heart rate, blood pressure, oxygen saturation, and perceived rating of exertion (RPE) were monitored at each stage of the protocol. Stress test results were reviewed by a cardiologist to determine whether exercise was safe for the individual or whether any underlying cardiac issues were present that needed further attention. Additionally, results from the stress test were used to measure each participant's resting heart rate and maximum heart rate (HR_{max}) to calculate individualized exercise intensity zones for the intervention. This test also served to estimate cardiorespiratory fitness based on the total test duration (details found in supplemental material). The 12-lead electrocardiogram test was repeated with each participant 6 months postintervention to assess changes in cardiorespiratory fitness.

Small Steps for Big Changes

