For full details regarding outcome measures of this trial, please refer to the trial registry details. Briefly, individuals' perceived autonomy support was measured post-intervention to discern any differences between conditions. Within-condition changes in motivation regulation from pre-intervention were assessed post-intervention and 6-months post-intervention. Within-condition changes in free-living physical activity and cardiorespiratory fitness were assessed from pre-intervention to 6-months post-intervention. Between-condition differences were also assessed at each timepoint for motivation regulation, physical activity, and cardiorespiratory fitness. A manipulation check was conducted with a sub-set of participants to determine the modality of exercise that participants engaged in during the 6-month follow-up period.

Changes Consequent to COVID-19

Recruitment for this trial commenced in February 2019 using a monthly rolling recruitment strategy (~6-10 participants/month). Originally, follow-up appointments were planned to discern changes in the outcome variables 12 months post-intervention. However, at the beginning of the 12-month follow-up phase (February 2020), the COVID-19 pandemic resulted in the curtailment of all research activities at the host institution. A total of 75 participants were not able to complete follow-up assessments, and data were therefore lost for this first cohort. Recruitment for this trial could not be resumed until October 2021. To complete data collection in a timely manner given these unanticipated resource constraints, follow-up assessments were conducted 6 months post-intervention for this second cohort as opposed to the original 12-month timepoint. The complete loss of data on the first 75 participants to enroll in the trial and subsequent curtailment of research for more than 1.5 years therefore significantly limited the final study sample size.

Sample Size

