Limited studies have been conducted that assess perceived autonomy support after adults are provided a choice between different types of exercise in an intervention. A study by Lonsdale and colleagues assessed the change in perceived autonomy support among adolescents enrolled in physical education programs. Comparisons between the control group (treatment as usual) and a group that was provided choice in what exercises were performed during class demonstrated a small-to-medium effect favoring the choice group (d = 0.39). Based on these results, we anticipated a crude small-to-medium effect size in favor of the choice condition in the present study ($d = \sim 0.40$). At an alpha level of .05 and 80% power, we estimated that 60 participants per condition (n = 180) were required to detect significant between-condition differences at this magnitude. Based on pilot findings by Locke and colleagues, this sample size was then increased by 20% to account for participant attrition, resulting in a total sample size of 216. The severe COVID-19 pandemic limitations impacted the ability to achieve the estimated sample size and data are thus reported for N = 77.

Randomization

SSBC participants were randomly allocated into one of the three arms of this study in a 1:1:1 allocation ratio by using a computer random-number generator that produced variable permuted block sizes. Conditions were stratified for biological sex (male and female) and age (18-45 and 46-75 years). Allocation sequencing was performed by a member of the research team not involved in any other aspect of this trial and allocation was concealed from participants until they began the intervention.

Blinding

Given the pragmatic nature of this trial and the fact that participants and community coaches needed to know which exercise modality to engage in during the exercise sessions, blinding of participants and those delivering the intervention was not possible. Data collected for each participant were blinded during data analysis by replacing the name of the allocated condition with a numerical digit known only to a member of the research team not involved in the data analysis phase so that data analysts would not be biased by condition allocation.

Statistical Methods

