Statistical analyses were performed using R (version 4.3.0) or SPSS (version 28). Anthropometric and demographic information were summarized as means (standard deviations) for continuous data and N (%) for categorical data, unless otherwise stated. Medians and ranges are reported for 6-month exercise modality frequency to represent the central tendency and dispersion more accurately.

Blinded data analysis was completed on an intention-to-treat (ITT) basis as all randomized participants were included in the analyses irrespective of their program compliance. No missing data were imputed as per contemporary guidelines. A linear model with restricted maximum likelihood estimation (REML) was used to detect a between-condition difference in perceived autonomy support post-intervention. The model included treatment condition (i.e., HIIT, MICT, or CHOICE) as a fixed factor, and stratified allocation factors (i.e., age and biological sex) as covariates. Similarly, linear mixed models were used to analyze changes in motivation regulation, physical activity behavior, and cardiorespiratory fitness between conditions. Linear mixed models included fixed effects for timepoint (pre-intervention, postintervention, 6 months post-intervention), treatment condition, as well as the interaction thereof, stratified allocation factors, and a random effect for participants to address non-independence of measurements arising due to the repeated-measures design of this study. Model assumptions were assessed visually using normal probability plots and residuals vs. fitted values plots (i.e., homoscedasticity). Bonferroni-adjusted preplanned pairwise comparisons of estimated marginal means were conducted to derive effect estimates and accompanying 95% confidence intervals (CIs) after adjusting for included covariates. A two-sided alpha of .05 was used for all statistical analyses.

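### Does the unstated Bonferroni family for the mixed-model outcomes call for a change to the plan?

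*Combined protocol and SAP*

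**What the plan says.** The multiplicity rule is in the Statistical Methods section of the combined protocol and SAP: "Bonferroni-adjusted preplanned pairwise comparisons of estimated marginal means were conducted to derive effect estimates and accompanying 95% confidence intervals (CIs". The same section adds that "A two-sided alpha of .05 was used for all statistical analyses". It names no family and gives no divisor.

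The models for motivation regulation, physical activity and fitness are condition-by-time models: "Linear mixed models included fixed effects for timepoint (pre-intervention, postintervention, 6 months post-intervention), treatment condition, as well as the interaction thereof".

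The Outcomes section gives the comparisons of interest:

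- Between conditions: "Between-condition differences were also assessed at each timepoint for motivation regulation, physical activity, and cardiorespiratory fitness".
- Within conditions, motivation: "Within-condition changes in motivation regulation from pre-intervention were assessed post-intervention and 6-months post-intervention".
- Within conditions, activity and fitness: "Within-condition changes in free-living physical activity and cardiorespiratory fitness were assessed from pre-intervention to 6-months post-intervention".

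For fitness, the section on predicted maximal exercise testing supports two measurement occasions, one before the intervention and one later: "The 12-lead electrocardiogram test was repeated with each participant 6 months postintervention to assess changes in cardiorespiratory fitness". The Sample Size section states that "data are thus reported for N = 77".

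**The concern.** With one factor at one timepoint, as for perceived autonomy support, Bonferroni adjustment of pairwise comparisons plainly means three pairs and a divisor of 3. A condition-by-time model has no such single meaning. The analyst may adjust within each timepoint and within each condition, or across every comparison of the outcome, and both are ordinary practice.

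Under the narrower reading, a within-condition change in activity or fitness from baseline to 6 months is the only pair in its set. The adjustment then leaves it untouched, which a reader may not expect of a comparison described as Bonferroni-adjusted. If the divisor were 9 instead, the threshold would fall from .05 to .0056, so an unadjusted p-value between those limits would be significant under one reading and not under the other. With 77 participants and imprecise estimates, results in that band are plausible.

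**Working it through.** The document states no familywise error rate and no divisor, so there is no figure of the plan's own to reproduce on this point.

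**Inputs.** From the documents: three conditions allocated 1:1:1, two-sided alpha .05, N = 77, and one random participant effect. Assumed: arms of 26/26/25, complete data, within-participant correlation 0.3 to 0.8, one score per outcome, and no true difference or change anywhere.

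**Counts, from the Outcomes section.**

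- Motivation regulation: 3 pairs × 3 timepoints + 2 changes × 3 conditions = 9 + 6 = 15.
- Activity and fitness: 3 pairs × 2 timepoints + 1 change × 3 conditions = 6 + 3 = 9 each.
- Perceived autonomy support: 3.

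The count of 9 depends on the Outcomes section. The model description lists three timepoints without exception. If activity were also measured just after the intervention, its count would be 3 × 3 + 3 = 12.

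**Familywise error per outcome.** Simulated from the random-intercept model, 40,000 trials per setting; ranges are over the assumed correlations.

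| Reading | Motivation (15) | Activity or fitness (9) |
|---|---|---|
| One family per outcome (divisor 15 or 9) | 3.9–4.4% | 3.9–4.3% |
| Two families, between and within | 7.6–8.5% | 8.1–8.4% |
| Divisor 3 for every comparison | 16.6–18.6% | 11.1–11.9% |
| Within each timepoint (3) and each condition (2 or 1) | 20.2–21.7% | 19.1–19.6% |

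So 4% and 20% are the ends of a range, and the correlation hardly moves either end.

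**Where the upper figure comes from.** For activity or fitness, the three within-condition changes tested at .05 would alone give 1 − 0.95³ = 14.3% if independent; simulation gives 14.1%, out of about 19.5% in all. The rest includes pre-intervention comparisons between arms, where randomisation makes the null true and no treatment claim follows.

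**The randomised comparisons after baseline.** With divisor 3, the Bonferroni bound at one timepoint is 3 × (.05/3) = .05. For activity and fitness at 6 months the simulated rate is 4.2–4.4%. For motivation, with two post-baseline timepoints, the bound is 2 × .05 = .10 and the simulated rate 7.0–8.5%.

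**Effect on interval width.** Take SD 1 and 77/3 = 25.67 per arm.

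- Within-condition change, two timepoints, correlation 0.5: standard error = √[2(1 − 0.5)/25.67] = 0.197. With 74 degrees of freedom the 95% half-width is 0.39 SD at divisor 1 and 0.56 SD at divisor 9. Power for an illustrative 0.40 SD change is 52% and 21%. The effect of about 0.40 in the Sample Size section is a between-condition effect on autonomy support, so these powers do not relate to a planned target.
- Between conditions at one timepoint, motivation regulation: standard error = √(2/25.67) = 0.279. With 140 degrees of freedom the half-width is 0.68 SD at divisor 3 and 0.83 SD at divisor 15.

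**The case for a change.** The strongest argument for acting is that calling the comparisons preplanned implies a list, and the document gives none. The Outcomes section refers to the registry for outcome measures, which need not settle the multiplicity rule. The methods name R or SPSS without saying which was used for which analysis, so a software default cannot be inferred. Within-condition changes are stated targets, and a sentence per outcome would remove the doubt.

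The gap in the text is real, and so is the .0056 to .05 band if activity and fitness have two timepoints. Three things limit it.

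- The 20% requires that no arm changes on any occasion. All three arms receive supervised exercise and counselling, so that is a severe assumption for within-condition changes, which supply most of the figure for activity and fitness.
- The confidence intervals are less ambiguous than the divisor. The sentence on pairwise comparisons most naturally means that the intervals come from the adjusted comparisons.
- Control of familywise error across all comparisons of an outcome is a standard brought from outside. No section promises it, so the narrower reading breaks no commitment.

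The two timepoints in the Outcomes section and the three in the model description do not quite agree for activity. That affects the count, but a mixed model fits whichever occasions were measured.

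**Conclusion.** The concern does not call for a change. The document omits a detail that any competent analyst must settle to run the comparisons, and each ordinary way of settling it is valid. Naming the divisor would help a reader of the results, but it would alter no model, estimate or test. The document describes analyses already carried out, and replacing the adjustment once data have been seen would be worse than leaving it alone.

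For size: familywise error per outcome runs from about 4% to about 20% across readings, under a global null with complete data on 77 participants, near-equal arms, one score per outcome and correlations of 0.3 to 0.8. Counting only between-condition comparisons at divisor 3 per timepoint, baseline included, it is about 7–12%. With that divisor, the 6-month randomised comparison of activity or fitness is held at .05. Perceived autonomy support, the outcome on which the sample size was based, is untouched.

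### Single-step Bonferroni for the three pairwise condition comparisons is valid, but Tukey-Kramer intervals and a closed step-down test give somewhat more at the same familywise error

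*Combined protocol and SAP*

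**What the plan says.** For the primary model of perceived autonomy support, Statistical Methods states "The model included treatment condition (i.e., HIIT, MICT, or CHOICE) as a fixed factor", with age and sex as covariates. For the contrasts it states "Bonferroni-adjusted preplanned pairwise comparisons of estimated marginal means were conducted to derive effect estimates and accompanying 95% confidence intervals (CIs". It adds "A two-sided alpha of .05 was used for all statistical analyses". It names no step-down or joint-distribution method and does not say how many contrasts form a Bonferroni family.

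The Randomization section allocates to three arms "in a 1:1:1 allocation ratio". The Sample Size section says "we anticipated a crude small-to-medium effect size in favor of the choice condition in the present study", with d of about 0.40, and "At an alpha level of .05 and 80% power, we estimated that 60 participants per condition (n = 180) were required". After a 20% increase for attrition the target was 216. The same section ends by saying that "data are thus reported for N = 77". The split by arm is not given.

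**The concern.** With three pairs in the family, single-step Bonferroni requires p ≤ .05/3 = .0167 for every pair. For three means this is stricter than familywise control needs. If any two pairwise equalities hold, so does the third. The only hypotheses in the closed family are therefore the global null and the three single pairs. Once the global null has been rejected at .05, each remaining pair can be tested at .05.

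The question at stake is whether CHOICE differs from HIIT-only and from MICT-only on perceived autonomy support. With 77 participants against a target of 216, power is scarce. Bonferroni makes it somewhat more likely that a true advantage over both fixed arms is shown over only one of them, or over neither.

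**Working it through.** **The plan's own figure.** The plan gives no power for the adjusted contrasts, only 60 per condition. A two-sided unadjusted pairwise test needs n = 2(1.960 + 0.842)²/0.40² ≈ 98.1, so 99 per arm. At .05/3 it is 2(2.394 + 0.842)²/0.40² ≈ 130.9, so 131. The stated 60 is therefore not reproduced by a two-sided pairwise test. That is a separate and larger power problem; 60 per arm serves below only as a reference setting.

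**Inputs.** From the documents: three arms, 1:1:1, two-sided .05, d ≈ 0.40, N = 77, and 60 per arm as planned. Assumed: a 26/26/25 split, complete post-intervention data, three pairs in the family, and CHOICE above both fixed arms by the same amount, with HIIT-only equal to MICT-only. The primary model has five mean parameters (intercept, two for condition, age stratum, sex), so residual df = 77 − 5 = 72.

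**Critical values for |t| at 72 df.**
- Bonferroni: t(1 − .05/6) = 2.451
- Tukey: q(.95; 3, 72)/√2 = 2.393
- Unadjusted: t(.975) = 1.993

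Tukey intervals are 1 − 2.393/2.451 = 2.4% narrower.

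**Closed procedure.** Compare the largest |t| with 2.393. If it is rejected, compare the other two with 1.993. Because 2.393 < 2.451 and 1.993 < 2.451, every Bonferroni rejection is kept. Under the global null, a false rejection requires the Tukey gate to be passed (.05). If exactly one pair is truly equal, a false rejection requires that pair's own test to reject at .05. Familywise error is therefore controlled in every configuration.

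**Hand check of the Bonferroni column.** The noncentrality is d/√(1/26 + 1/26) = d/0.2774. For d = 0.40 it is 1.442, and Φ(1.442 − 2.451) = Φ(−1.009) ≈ 16%. For 0.8 SD it is 2.884, and Φ(2.884 − 2.451) = Φ(0.433) ≈ 67%. Both agree with the simulation.

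**Simulation** (400,000 replicates, pooled-variance t tests):

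| Setting | Power for | Bonferroni | Tukey-gated step-down | Gain (points) |
|---|---|---|---|---|
| N = 77, d = 0.40 | at least one CHOICE difference | 26% | 28% | 2 |
| N = 77, d = 0.40 | a given CHOICE pair | 16% | 21% | 5 |
| N = 77, d = 0.40 | both CHOICE pairs | 7% | 13% | 6 |
| 60 per arm, d = 0.40 | a given CHOICE pair | 41% | 50% | 9 |
| 60 per arm, d = 0.40 | both CHOICE pairs | 25% | 40% | 15 |
| N = 77, 0.8 SD | a given CHOICE pair | 67% | 76% | 9 |
| N = 77, 0.8 SD | both CHOICE pairs | 51% | 68% | 17 |

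The gain in the first row comes from the Tukey critical value. A step-down that starts at .05/3 (Shaffer) adds essentially nothing to the chance of a first rejection. Simulated familywise error for the step-down was about .05 or below, under the global null and when one pair is truly equal. For Bonferroni it was about .043 under the global null.

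**Chance of finding a CHOICE advantage over one fixed arm only**, at N = 77 and d = 0.40: 26 − 7 = 19% under Bonferroni, and about 28 − 13 = 15% under the step-down.

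**The case against.** The strongest defence is that the quoted sentence is about estimation. Bonferroni gives simple intervals that always agree with its tests, and on intervals alone the improvement is only 2.4% in width. Step-down rejections come at a price: when the step-down starts at .05/3, 86% to 90% of the extra rejections at N = 77 have a Tukey interval that includes zero. Starting at the Tukey value removes the mismatch at the first step, but most of the additional second- or third-pair rejections still have this feature. This stands, and the plan would have to say so.

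Second, the document is in the past tense and calls the comparisons preplanned. Moving to a more liberal rule once results are known would be a post hoc change. This also stands, but it governs how the new analysis is reported, not whether Bonferroni is dominated.

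Third, the family is not defined. The Outcomes section also lists within-condition changes over time, and the argument here covers only three conditions at one timepoint. The figures depend on that reading.

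A reader might go further and infer that this trial gives up some 9 to 17 points of power, or that Bonferroni is a mistake. The documents support neither. Gains of that size need the unattained 60 per arm, or an effect of 0.8 SD, twice the one planned. At N = 77 and d = 0.40 the gain is 2 to 6 points, depending on how power is defined.

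**Conclusion.** The point holds as an optional efficiency improvement. Single-step Bonferroni controls familywise error and is not an error, but for three conditions it is dominated for both tests and intervals. At the trial's own N and effect size the benefit is small in absolute terms, although power to show both CHOICE differences nearly doubles, from 7% to 13%. Even with the change, power at N = 77 and d = 0.40 stays low, so the change does not remedy the lost sample. The figures rest on the assumed split, on a three-pair family at one timepoint, and on equal fixed-arm means.

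**What to change.** For between-condition contrasts, in the autonomy-support model and at each timepoint of the mixed models, replace the Bonferroni wording with text such as: 'Pairwise differences between the three conditions are reported with Tukey-Kramer (multivariate t) simultaneous 95% CIs. For p-values, the largest |t| is compared with the Tukey critical value; if it is rejected, the other two pairs are each tested at two-sided .05. The step-down p-value governs the test and the simultaneous interval governs estimation; for a second or third pair, a rejection may accompany an interval that includes zero.'

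State that the family is the three condition pairs at one timepoint, and leave the within-condition changes over time outside this rule. If results are already known, keep the preplanned Bonferroni results and show these beside them as a sensitivity analysis.

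The cost is a few lines of SAP wording and a rerun of the contrast step, with no new data. The price in interpretation is the possible disagreement between test and interval, which the wording above discloses.
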